7. TREATMENTS

Study treatment is defined as any investigational treatment(s), marketed product(s), placebo, or medical device(s) intended to be administered to a study participant according to the study protocol. The term 'study treatment' within this trial is used to describe the combination of products received by the participant as per the protocol design. Study treatment may also be used to only reference the randomized study treatment when described together with the FF 100 mcg open-label treatment.

7.1. Treatments Administered

7.1.1. Description of FF 100 mcg and Double-Blind Study Treatment

The ELLIPTA device will be used during the run-in period and the treatment period. The ELLIPTA dry powder inhaler (DPI) is a molded plastic two-sided device with a dose counter that can hold two individual blister strips. The ELLIPTA will deliver, when actuated, the contents of a single blister simultaneously from each of the two strips. The ELLIPTA is individually sealed in a foil laminate overwrap that also contains a silica gel desiccant packet.

A description of the FF (GW685698) 100 mcg inhalation powder administered via the ELLIPTA is provided in [Table 1](#); descriptions of the double-blind study treatments administered via the ELLIPTA are provided in [Table 2](#).

Table 1 Description of FF 100 mcg Inhalation Powder in ELLIPTA

FF 100	First Strip	Second Strip
	GW685698 blended with lactose monohydrate	Lactose monohydrate with magnesium stearate ¹
Dosage Form	ELLIPTA DPI with 30 doses (2 strips with 30 blisters)	
Unit Dose strengths	100 mcg per blister	Not applicable
Physical description	White powder	White powder
Route of Administration	Inhaled	

1. Magnesium stearate 1.0% w/w of total drug product.

Table 2 Description of Study Treatment Inhalation Powder in ELLIPTA

Placebo	First strip	Second strip
	Lactose monohydrate blended with magnesium stearate ¹	Lactose monohydrate blended with magnesium stearate ²
Dosage Form	ELLIPTA DPI with 30 doses (2 strips with 30 blisters per strip)	
Unit Dose Strengths	Not applicable	Not applicable
Physical description	White powder	White powder
Route of Administration	Inhaled	
UMEC	First strip	Second strip
	GSK573719 blended with lactose and magnesium stearate ²	Lactose monohydrate blended with magnesium stearate ²
Dosage Form	ELLIPTA DPI with 30 doses (2 strips with 30 blisters)	
Unit Dose Strengths	31.25 mcg per blister	NA
Physical description	White powder	White powder
Route of Administration	Inhaled	
UMEC	First strip	Second strip
	GSK573719 blended with lactose and magnesium stearate ²	Lactose monohydrate blended with magnesium stearate ²
Dosage Form	ELLIPTA DPI with 30 doses (2 strips with 30 blisters)	
Unit Dose Strengths	62.5 mcg per blister	NA
Physical description	White powder	White powder
Route of Administration	Inhaled	

1. Magnesium stearate 0.6% w/w of total drug product. 2. Magnesium stearate 1.0% w/w of total drug product

7.1.2. Description of Albuterol/Salbutamol

Albuterol/salbutamol via metered-dose inhaler (MDI) will be issued for reversibility testing at Visit 1. An albuterol/salbutamol MDI for as needed (prn) use throughout the study will be provided starting at Visit 1; at the Investigator's discretion, more than one MDI may be provided at any one time. Albuterol/salbutamol will be sourced from local commercial stock. If not available locally, GSK will source centrally. The contents of the label will be in accordance with all applicable regulatory requirements.

7.1.3. Study Treatment, albuterol/salbutamol, and FF 100 mcg Return

ELLIPTAs containing FF 100 mcg, and study treatment, in addition to albuterol/salbutamol, will be dispensed to a participant during their visit to the study clinic (as applicable). The participant must return all dispensed ELLIPTAs and albuterol/salbutamol at the subsequent clinic visit. The schedule for dispensing and collecting FF 100 mcg and study treatment ELLIPTAs is provided in the Schedule of Activities table (Section 2).

All used and unused study treatment, FF 100 mcg and albuterol/salbutamol will be returned to GSK at the end of the study to be available for disposal. In some instances, for sites outside the US, study supplies will be disposed of locally either by the site, the country medical department or third-party vendor. Detailed instructions for the return of the study drug can be found in the Study Reference Manual (SRM).

If any ELLIPTA fails to function properly, the participant should return to the clinic as soon as possible to obtain a new inhaler. The site will use the IWRS (RAMOS NG) to obtain a new treatment pack number for the participant and dispense a new study treatment kit from the site's study treatment supply as instructed by the IWRS.

In addition, any metered dose inhaler (MDI) that fails to function properly must be identified and returned to GSK for testing. Details of the failure will be documented in the eCRF.

7.2. Dose Modification

There were no dose modifications planned for this protocol.

7.3. Method of Treatment Assignment

Participants will be assigned to study treatment in accordance with the randomization schedule. The randomization code will be generated by GSK using a validated computerized system. Participants will be randomized using an interactive web response system (IWRS) RAMOS NG. The study will use central-based randomization to allocate treatments. Once a randomization number is assigned to a participant it cannot be reassigned to any other participant in the study.

Following the 2-week run-in period and participant to satisfying all eligibility criteria, participants will be randomized 1:1:1 to one of the following three double-blind treatments for the duration of the treatment period:

- UMEC 62.5 mcg QD
- UMEC 31.25 mcg QD
- Placebo QD

The duration of double-blind treatment for each participant is 24 weeks. On the morning of each scheduled clinic study visit, participants will refrain from taking their morning dose of study treatment and FF 100 mcg until instructed to do so by clinic personnel. Study treatment will be taken at the clinic at approximately the same time of day as taken at the Randomization Visit (Visit 2). On the other days during the treatment period (i.e. “non-clinic days”), participants will be instructed to take their study treatment each morning at approximately the same time. Each Investigator will be provided with sufficient supplies to conduct the trial. Additional treatment packs will be supplied as needed to the sites. Details of how to use the IWRS system (RAMOS NG) to randomize participants and manage study treatment supplies (including dispensing) is provided in the RAMOS NG IWRS manual and SRM.

7.4. Blinding

This will be a double-blind study and the following will apply.

- The Investigator or treating physician may unblind a participant’s treatment assignment only in the case of an emergency OR in the event of a serious medical condition when knowledge of the study treatment is essential for the appropriate clinical management or welfare of the participant as judged by the Investigator.
- Investigators have direct access to the participant’s individual study treatment.
- It is preferred (but not required) that the Investigator first contacts the Medical Monitor or appropriate GSK study personnel to discuss options before unblinding the participant’s treatment assignment.
- If GSK personnel are not contacted before the unblinding, the Investigator must notify GSK within 24 hours after unblinding, but without revealing the treatment assignment of the unblinded participant, unless that information is important for the safety of participants currently in the study.
- The date and event or condition which led to the unblinding (i.e. the primary reason) will be recorded in source documentation and in the eCRF.

Should a participant’s treatment assignment be unblinded then the participant may continue the assigned study treatment and be followed-up as per protocol until the completion of the Safety Follow-up assessments.

GSK’s Global Clinical Safety and Pharmacovigilance (GCSP) staff may unblind the treatment assignment for any participant with an SAE. If the SAE requires that an expedited regulatory report be sent to one or more regulatory agencies, a copy of the report, identifying the participant’s treatment assignment, may be sent to Investigators in accordance with local regulations and/or GSK policy. Participants will not be withdrawn from the study.

7.5. Packaging and Labeling

The contents of the label will be in accordance with all applicable regulatory requirements.

7.6. Preparation/Handling/Storage/Accountability

1. The investigator or designee must confirm appropriate temperature conditions have been maintained during transit for all study treatment received and any discrepancies are reported and resolved before use of the study treatment.
2. Only participants enrolled in the study may receive study treatment and only authorized site staff may supply or administer study treatment. All study treatments must be stored in a secure, environmentally controlled, and monitored (manual or automated) area in accordance with the labeled storage conditions with access limited to the investigator and authorized site staff.
3. The investigator, institution, or the head of the medical institution (where applicable) is responsible for study treatment accountability, reconciliation, and record maintenance (i.e., receipt, reconciliation, and final disposition records).
4. Further guidance and information for the final disposition of unused study treatment are provided in the SRM.
5. Under normal conditions of handling and administration, study treatment is not expected to pose significant safety risks to site staff. Take adequate precautions to avoid direct eye or skin contact and the generation of aerosols or mists. In the case of unintentional occupational exposure notify the monitor, Medical Monitor and/or GSK study contact.
6. A Material Safety Data Sheet (MSDS)/equivalent document describing occupational hazards and recommended handling precautions either will be provided to the investigator, where this is required by local laws, or is available upon request from GSK.

7.7. Treatment Compliance

When participants are dosed at the site, they will receive FF 100 mcg and study treatment under medical supervision. The date and time of each dose administered in the clinic will be recorded in the eCRF. The dose of study treatment and study participant identification will be confirmed at the time of dosing by a member of the study site staff.

When participants self-administer study treatment(s) at home, compliance with study treatment will be assessed through querying the participant during the site visits and recording the number of doses remaining in the ELLIPTA in the eCRF (see the SRM for details). A record of the number of ELLIPTAs dispensed to each participant must be maintained and reconciled with study treatment and compliance records.

Participant compliance with FF 100 mcg and study treatment will be assessed at scheduled clinic visits by reviewing the eDiary and information from the dose counter on the returned inhaler(s) (see Section 7.1.3). Participants should be $\geq 80\%$ to $\leq 120\%$ compliant on taking both FF 100 mcg and study treatment between each pair of

compliant on taking both FF 100 mcg and study treatment between each pair of scheduled and consecutive on-treatment clinic visits, as applicable. Participants who fall outside this range should be re-educated on treatment compliance by their site. This re-education should be documented in the participant's source document. If FF 100 mcg and/or study treatment is prematurely discontinued during the course of the study or compliance repeatedly falls outside of acceptable ranges, the study sponsor/site monitor must be contacted to discuss participant eligibility for continued participation in the study.

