- **Safety follow-up:** A safety follow-up telephone contact or clinic visit will be conducted approximately 7 days after the participant completes all of the protocol-defined procedures for Visit 5/End of Study (EOS) or, if applicable, the Early Withdrawal Visit. A participant will be considered to have completed the study when they have completed all phases of the study including screening, run-in, the randomized treatment phase, and safety follow-up.

To demonstrate the benefit of UMEC the primary comparisons of interest for the primary efficacy endpoint are:

- UMEC 62.5 mcg versus (vs) Placebo
- UMEC 31.25 mcg vs Placebo

Other pairwise treatment comparisons of interest that aim to informally estimate any potential benefit of increasing the UMEC dose are given below for all efficacy endpoints.

- UMEC 62.5 mcg vs UMEC 31.25 mcg

For the multiple comparisons and multiplicity adjustment, please see Section 10.5.3. Participants who permanently discontinue double-blind study treatment are not required to withdraw from the study. Participants who have permanently discontinued study treatment and have not withdrawn consent are encouraged to continue in the study and complete all remaining protocol specified clinic visits (see Section 8.1)

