8. DISCONTINUATION CRITERIA

8.1. Discontinuation of Study Treatment

Participants that permanently stop study treatment are encouraged to remain in the study. Participants have the right to discontinue study treatment before the end of the study. A participant may also be asked to discontinue study treatment at the Investigator's discretion.

Participants who withdraw from study treatment prematurely (for any reason) should, where possible, continue to be followed-up as per protocol until the completion of the Safety Follow-up assessments. If this is not possible, the Investigator must encourage the participant to participate in as much of the study as they are willing (or able) to.

A participant may be withdrawn from study treatment at any time. A reason for premature discontinuation of study treatment (e.g., AE, lack of efficacy [including moderate or severe asthma exacerbation], protocol deviation, Investigator discretion, consent withdrawn etc.) must be captured in the eCRF.

A participant must be withdrawn from study treatment if any of the following stopping criteria are met:

- Liver Chemistry: Meets any of the protocol-defined liver chemistry stopping criteria
- QTc: Meets any of the protocol-defined stopping criteria
- Pregnancy: Positive pregnancy test

[figure not shown]

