8.2. Withdrawal from the Study

- A participant may withdraw from the study at any time at his/her own request, or may be withdrawn at any time at the discretion of the investigator for safety, behavioral, compliance or administrative reasons.
- If the participant withdraws consent for disclosure of future information, the sponsor may retain and continue to use any data collected before such a withdrawal of consent.
- If a participant withdraws from the study, he/she may request destruction of any samples taken and not tested, and the investigator must document this in the site study records.
- In the event of early withdrawal from the study, every effort should be made to have the participant to return to the clinic for an Early Withdrawal Visit and Safety Follow-up, and to return all study related materials. Assessments to be performed during the Early Withdrawal Visit and the Safety Follow-up contact are described in the Schedule of Activities table (Section 2).

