10.6.1. Primary Analyses

The primary efficacy endpoint is the mean change from baseline in trough FEV₁ at the end of the 24-week treatment period. For each participant, the baseline value of clinic FEV₁ is the last acceptable/borderline acceptable (pre-dose) FEV1 value obtained prior to randomization (either from Visit 2 pre-dose or from Visit 1 pre-bronchodilator).

The primary efficacy analysis will evaluate the “de facto” type estimand in the Intent-to-Treat population, using a mixed-model repeated measures (MMRM) analysis, including all trough FEV₁ recorded post randomization. Analyses will include the fixed, categorical effects of treatment, visit, treatment by visit interaction, sex, as well as the continuous, fixed covariates of age, baseline value, and baseline value by visit interaction. Point estimates and 95% confidence intervals will be calculated for the following primary comparisons of interest.

- UMEC 62.5 mcg vs Placebo
- UMEC 31.25 mcg vs Placebo

In addition, a de jure estimand, including data collected over the randomized double-blind treatment period, will be analyzed using a MMRM model. Sensitivity analyses to assess the impact of missing data will be detailed in the RAP.

Other pairwise treatment comparisons of interest as outlined in Section 10.5.2 will also be provided for the primary efficacy endpoint.

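### Sections 7.7 and 8.2 leave room to end study follow-up after treatment discontinuation or for poor compliance, in tension with 5.1 and 8.1, and may lose trough FEV1 that the de facto primary analysis is meant to include

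*Protocol*

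**What the plan says.** **Retention.** Section 5.1 states: "Participants who permanently discontinue double-blind study treatment are not required to withdraw from the study". It adds: "Participants who have permanently discontinued study treatment and have not withdrawn consent are encouraged to continue in the study". Section 8.1 says the same more broadly: "Participants who withdraw from study treatment prematurely (for any reason) should, where possible, continue to be followed-up as per protocol", through to the Safety Follow-up.

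**Compliance and withdrawal.** Section 7.7 sets a compliance range of 80% to 120% between consecutive visits, for both FF 100 mcg and study treatment. The first response is re-education: "Participants who fall outside this range should be re-educated on treatment compliance by their site". The section then names two triggers for a further step. One is early discontinuation: "If FF 100 mcg and/or study treatment is prematurely discontinued during the course of the study or". The other is compliance that is repeatedly out of range. In either case "the study sponsor/site monitor must be contacted to discuss participant eligibility for continued participation in the study". Section 8.2, which concerns leaving the study rather than leaving treatment, says a participant "may be withdrawn at any time at the discretion of the investigator for safety, behavioral, compliance or administrative reasons".

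**Analysis.** Section 10.6.1 defines the primary analysis as a de facto "type estimand in the Intent-to-Treat population, using a mixed-model repeated measures (MMRM) analysis" that takes in all trough FEV1 recorded after randomization. A de jure analysis, limited to the double-blind treatment period, is planned in addition. Section 10.2 allows for 10% missing Week 24 spirometry and attributes it to early withdrawal from the study.

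**The concern.** A de facto estimand needs outcome data from people after they stop treatment. Sections 5.1 and 8.1 are written to obtain those data. Section 7.7 takes the same event, stopping treatment, and attaches to it a question about staying in the study, where one would expect a question about staying on treatment. Section 8.2 then gives the investigator compliance as a reason for ending study participation altogether. A site that acts on 7.7 and 8.2 could therefore close follow-up for participants whom 5.1 and 8.1 want to keep.

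Losses of this kind would be selective. They would fall on people who are off drug or poorly adherent, and 8.1 lists lack of efficacy, including exacerbation, among the reasons for stopping treatment, so the losses may be related to outcome. The MMRM would then in effect predict the missing Week 24 values from participants who stayed, most of them on drug. The estimate labelled de facto could move toward the de jure one. An analysis plan cannot repair this afterwards, because it cannot recover measurements that were never taken.

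**Working it through.** **1. The passages side by side**

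| Section | Event | Consequence for being in the study | Force |
|---|---|---|---|
| 5.1 | Double-blind treatment stopped | Need not leave; complete remaining visits | Encouraged |
| 8.1 | Treatment stopped, any reason | Follow-up continues to Safety Follow-up | Should, where possible |
| 7.7 | FF or study treatment stopped, or compliance repeatedly out of range | Eligibility to stay in the study is put up for discussion | Contact is mandatory; outcome not stated |
| 8.2 | Compliance reasons | Participant may be withdrawn from the study | Investigator discretion |

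The sharpest tension is between 7.7 and 8.1. Under 8.1 the reason for stopping does not matter to follow-up; under 7.7 the act of stopping opens the question of whether follow-up goes on. In 8.2 the point of tension is the single word compliance. Stopping treatment is not listed there.

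**2. When data could be lost**

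The Schedule of Activities assesses double-blind compliance at Visits 3, 4 and 5 (Weeks 4, 12 and 24). If repeatedly means at least two intervals, the compliance trigger cannot be met before Visit 4, and what is at risk is the Week 24 value, the primary time point. If it is first met at Visit 5, no trough value is lost. The discontinuation trigger can occur at any time, so later visits as well as Week 24 may be at risk. The Early Withdrawal Visit includes spirometry, but it measures FEV1 when the participant leaves, not at Week 24.

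**3. The plan's own figures (Section 10.2)**

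Inputs: difference 130 mL, SD 350 mL, two-sided 5%, 115 evaluable and 128 randomized per arm, 10% missing.

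- Standard error: 350 × √(2/115) = 46.16 mL.
- Power: Φ(130/46.16 − 1.96) = Φ(0.857) = 0.804; with the t distribution, 0.801. Stated: 80%.
- Smallest significant difference: 1.96 × 46.16 = 90.5 mL. Stated: 90.5 mL.
- Randomized: 115/0.90 = 127.8, rounded up to 128 per arm; × 3 = 384. Stated: 384.

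All reproduce, and this point does not dispute them.

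**4. Illustration of lost precision**

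The documents give no rate of withdrawal under 7.7 or 8.2. The missing rates other than 10% are assumptions. Evaluable n = 128 × (1 − missing rate); power = Φ(130/(350 × √(2/n)) − 1.96).

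| Missing at Week 24 | n per arm | Power |
|---|---|---|
| 5% | 121.6 | 0.825 |
| 10% (plan) | 115.2 | 0.805 |
| 15% | 108.8 | 0.782 |
| 20% | 102.4 | 0.757 |

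The loss of precision is modest. Bias is the more important consequence, and nothing in the documents allows it to be sized.

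**The case against.** The strongest reply is that the protocol's governing text favours retention. Section 7.7 asks for a conversation and names no outcome; a sponsor contacted under it would have 5.1 and 8.1 to apply. Section 8.2 says only that a participant may be withdrawn. Section 7.4, after unblinding, and Appendix 7, after a liver stopping event, also allow follow-up to continue. Section 10.6 includes data from people who withdraw, where possible, and 10.6.1 promises sensitivity analyses for missing data, with details in an analysis plan that is not shown.

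Most of this stands, and it rules out several stronger readings:

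- **That stopping treatment is a ground for leaving the study, or that 7.7 says the opposite of 8.1.** It is not a stated ground anywhere, and 5.1 and 8.1 are themselves soft (encouraged, where possible).
- **That the plan, followed as written, removes off-treatment data or uses up the 10% allowance.** The documents give no number for withdrawals through this route. The 10% covers all early study withdrawal.
- **That the primary estimate is overstated by a given number of mL.** A reader might compute 10% × 130 = 13 mL. That requires every missing participant to have come through this route, all of them to have lost the whole effect, and the MMRM to credit all of them with the full on-drug effect. None of this is in the documents. The compliance trigger also covers use above 120%, where total loss of effect is not a natural assumption. If losses differ by arm, the direction could differ too.

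What the reply does not remove is the wording. Section 7.7 still makes study participation the subject of the discussion, and 8.2 still names compliance. Including withdrawn participants' data helps only where the data exist, and sensitivity analyses examine assumptions about missing values without restoring them.

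**Conclusion.** The point holds as a matter of wording with a plausible statistical consequence. Sections 7.7 and 8.2 allow the sponsor or investigator to end study participation after treatment discontinuation or for non-compliance. That is in tension with 5.1 and 8.1 and with a primary analysis meant to include post-discontinuation FEV1. The result may be lost Week 24 values and a de facto estimate that moves toward the de jure one.

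The size is unknown. The only figure that can be offered is conditional: if withdrawals of this kind raised missing data from 10% to 15%, power per comparison would fall from about 0.80 to 0.78 under the plan's own 130 mL and 350 mL, counting only participants with a Week 24 value. The stated sample size is not in question. This is an inexpensive improvement worth making, not a flaw that undermines the design.

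**What to change.** Reconcile 7.7 and 8.2 with 5.1 and 8.1 in two places.

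- **Section 7.7:** keep the contact with the sponsor or monitor, but state that neither discontinuation of FF or study treatment nor non-compliance by itself ends scheduled data collection.
- **Section 8.2:** remove compliance as a stand-alone ground for withdrawal from the study, and refer such cases to 8.1.

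Leave the safety and administrative grounds in 8.2 in place; the administrative ground is needed, for example, for the site closure provided for in Appendix 3. Withdrawal of consent, loss to follow-up (Section 8.3) and all decisions on dosing or on continuing treatment are untouched.

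The cost is two wording changes in an amendment, a memo to sites, and a few more off-treatment visits. No sample size or analysis figure changes.
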